#### 4.6 Toxicity Management

In response to AEs reported by study participants and/or observed upon exam by study staff, the investigator or designee will recommend either continuation or discontinuation of product use consistent with the criteria in Appendix III. Product use also will be discontinued in the event of pregnancy.

Participants who discontinue product use will not routinely be withdrawn from the study. Rather, every effort will be made to complete the safety evaluations scheduled to take place on study Days 7 and 14.

#### 4.7 Concomitant Medications

Enrolled participants may continue use of all concomitant medications — except exclusionary preparations applied to the external genitalia or inserted into the vagina — during this study. All concomitant medications will be recorded on applicable study case report forms. Medications used for the treatment of AEs that occur during study participation also will be recorded on applicable case report forms.

#### 5.0 Study Procedures

Presented in Sections 5.1-5.5 are the clinical and laboratory procedures to be conducted at individual participant study visits. These procedures also are summarized in Appendices I and II. Focus group procedures are described in Section 5.8.

#### 5.1 Screening Visit for Female Participants (up to Day –30)

Potential participants will be screened for presumptive eligibility for the study according to the procedures described below. All procedures will be completed in a step-wise manner for potential participants who meet the study eligibility criteria. For participants who do not meet the eligibility criteria, screening will be discontinued when ineligibility is determined. For potential participants who are found to be presumptively eligible at this visit, final eligibility will be confirmed at an Enrollment Visit scheduled to take place within 30 days of screening.

### 5.1.1 Clinical Procedures

- Obtain informed consent.
- Assign Participant ID.
- Collect demographic and locator information.
- Collect medical history and concomitant medication information.
- Provide HIV and STD pre-test and risk reduction counseling.
- Collect urine for HCG pregnancy test; provide participant with result.
- Collect urine for dipstick urinalysis (if symptomatic) and process urine culture if dipstick positive for urinary tract infection (UTI).
- Collect urine for *N. gonorrhoeae* and *C. trachomatis* LCR assay.
- Perform pelvic examination including:
  - speculum examination of vagina and cervix,
  - collect pH sample from the vaginal wall,
  - collect swab from anterior or lateral fornix for:
    - one dried smear (smear specimen on slide and allow to air dry),
    - wet prep (two samples of discharge on slide for saline prep, potassium hydroxide prep and whiff test), and
  - if ulcerative lesions are noted, collect swabs for syphilis dark field microscopy (on-site) and Multiplex PCR (M-PCR) for HSV-2, *H.ducreyi*, and *T. pallidum* (at the HPTN Central Lab),
  - collect ectocervical and endocervical specimen for Pap smear (if no documented normal Pap within the past three months), and
  - bimanual examination for adnexal masses or tenderness.
- Collect blood for HIV, syphilis serology, hematology, liver and renal function, APTT/PT.
- Schedule Enrollment Visit to occur 2-7 days post next menses.

- Instruct participant to abstain from sexual intercourse beginning 48 hours prior to the Enrollment Visit.
- Provide practice Daily Study Records and instructions for completion.
- Complete all required data collection forms.

# 5.1.2 Laboratory Procedures

- Record results of urine pregnancy test.
- Record results of dipstick urinalysis and process urine culture if dipstick positive for UTI.
- Record vaginal pH measurement.
- Examine wet mount by direct microscopy to detect *T. vaginalis*, *C. albicans* infections, and clue cells for BV.
- Conduct LCR for *N. gonorrhoeae* and *C. trachomatis*.
- Conduct dark field microscopy of swab of ulcerative lesion, if collected.
- Send swab specimen to the HPTN Central Lab for M-PCR, if symptomatic.
- Store unstained dried smear for Gram staining and batch analysis using the Nugent criteria for BV.
- Prepare and read Pap smear if required.
- Conduct EIA test (with confirmation for positives) for HIV.
- Conduct RPR with confirmation by FTA-ABS or TP/HA for *T. pallidum*.
- Conduct complete blood count, APTT/PT, liver and renal function tests.

#### 5.2 Enrollment Visit for Female Participants (Day 0)

Female participants who are found to be presumptively eligible at their Screening Visits will complete Enrollment Visits 2-7 days post-menses, and within 30 days after the Screening Visit. Female participants who do not complete an Enrollment Visit within 30 days of screening must repeat the screening process.

All female participants will receive their screening test results at their Enrollment Visits. For those whose test results meet the study eligibility criteria, the procedures below will be undertaken in a step-wise manner to confirm eligibility. As was the case at the Screening Visit, the procedures will be discontinued if ineligibility is determined at this visit.

# 5.2.1 Clinical Procedures

- Update locator information.
- Provide results of HIV and STD tests and post-test counseling.
- Review practice Daily Study Records for completeness and accuracy.
- Document that the participant's partner has provided informed consent.
- Complete Initial Acceptability Assessment.
- Collect urine for HCG pregnancy test; provide participant with result.
- Collect urine dipstick urinalysis (if symptomatic) and process urine culture if dipstick positive for urinary tract infection (UTI).
- If symptomatic, collect urine for *N. gonorrhoeae* and *C. trachomatis* LCR assay.
- Perform pelvic examination with colposcopy (according to Appendix V) including:
  - speculum examination of vagina and cervix,
  - colposcopic examination of the vulva, vaginal and cervical mucosa,
  - take baseline colposcopic digital image(s) without filter, encompassing the cervix and fornices,
  - collect pH sample from the vaginal wall,
  - collect swab from anterior or lateral fornix for:
    - one dried smear (smear specimen on slide and allow to air dry),
    - wet prep (two samples of discharge on slide for saline prep, potassium hydroxide prep and whiff test), and
  - ➢ if ulcerative lesions are noted
    - photograph lesions according to procedures in Appendix V
    - collect swabs for syphilis dark field microscopy (on-site) and M-PCR for HSV-2, *H.ducreyi* and *T. pallidum* (at the HPTN Central Lab)
    - collect blood for syphilis serology
  - bimanual examination for adnexal masses or tenderness.
- Collect blood for hematology, liver and renal function, APTT/PT, PRO 2000/5 analysis and plasma and serum archive.
- Provide instructions for product administration (see Appendix IV).
- Observe first product administration (if desired by participant).
- Provide Daily Study Records and instructions for completion.
- Count and record total number of tubes of study product dispensed to the study participant.
- Distribute study product and applicators (2 kits), condoms and panty liners.
- Instruct participant to return all used and unused tubes and applicators to the clinic at her Day 2 visit.

- Instruct participant on anticipated amount, consistency and color of discharge due to gel expulsion.
- Instruct participant to distinguish between discolored or malodorous discharge and the discharge anticipated with use of study product.
- Instruct participant to contact or return to the study site if she experiences discomfort, discolored or malodorous discharge, or other AEs.
- Administer Behavioral Assessment Questionnaire
- Schedule Day 2 Follow-up Visit.
- Label digital image with location/image number.
- Complete all required data collection forms.

### 5.2.2 Laboratory Procedures

- Record results of urine pregnancy test.
- Record results of dipstick urinalysis and process urine culture if dipstick positive for UTI.
- Record vaginal pH measurement.
- Examine wet mount by direct microscopy to detect *T. vaginalis*, *C. albicans* infections, and clue cells for BV.
- Conduct LCR for *N. gonorrhoeae* and *C. trachomatis* if symptomatic.
- If ulcerative lesion was observed, conduct dark field microscopy of swab and serology (RPR with confirmation by FTA-ABS or TP/HA) for *T. pallidum* and prepare and ship swabs to the HPTN Central Lab for M-PCR.
- Store unstained dried smear for Gram staining and batch analysis using the Nugent criteria for BV.
- Conduct complete blood count, APTT/PT, liver and renal function tests.
- Prepare plasma samples for determination of study drug levels for batch shipping at the end of the study.
- Archive plasma and serum.

# 5.3 Screening/Enrollment Visit for Male Participants Only (Day –30 to Day 0)

- Obtain written informed consent.
- Collect demographic and locator information.
- Collect information on STD history during the past three months and current STD symptoms. If current symptoms are reported, offer exam and clinically appropriate STD work-up.
- Provide HIV pre-test counseling.
- Collect blood for HIV serology, and
- Deliver test results and post-test counseling when results are available.

- Provide the participant with:
  - > instructions regarding the study behavioral requirements, and
  - instructions to contact study staff to ask questions and/or report AEs.

# 5.4 Day 2 Follow-Up Visit for Female Participants

This visit is scheduled to take place on study Day 2. As described below, the baseline evaluations completed at the study Screening and Enrollment Visits are repeated at this visit. Diagnosis and follow-up of any observed abnormalities will proceed according to Appendix III.

# 5.4.1 Clinical Procedures

- Update locator information.
- Review Daily Study Records and note the time of last product application; review instructions for completion of Daily Study Records if needed.
- Count used and unused product tubes and conduct adherence interview. Store used tubes until end of study. If space does not allow storage, then document the count and disposal.
- Perform pelvic examination with colposcopy (according to Appendix V) including:
  - > speculum examination of vagina and cervix
  - colposcopic examination of the vulva, vaginal and cervical mucosa
  - take colposcopic digital image(s) encompassing the cervix and fornices
  - collect pH sample from the vaginal wall
  - collect swab from anterior or lateral fornix for:
    - one dried smear (smear specimen on slide and allow to air dry)
    - wet prep (two samples of discharge on slide for saline prep potassium hydroxide prep and whiff test) and
  - bimanual examination for adnexal masses or tenderness
  - ➢ if abnormal vaginal discharge or purulent cervicitis is noted, collect urine for *N. gonorrhoeae* and *C. trachomatis* LCR assay.
  - ➢ if ulcerative lesions are noted:
    - Photograph lesions according to procedures in Appendix V.
    - collect swabs for syphilis dark field microscopy (on-site) and M-PCR for HSV-2, H.*ducreyi* and *T. pallidum* (at the HPTN Central Lab)
- If symptomatic, collect urine for dipstick urinalysis.
- Provide instruction for follow-up care and product use, or not, as appropriate .

- Instruct participant to contact or return to the study site if she experiences discomfort, discolored or malodorous discharge or other AEs.
- Distribute additional study supplies (e.g., condoms, panty liners) if needed.
- Schedule Day 7 Follow-up Visit.
- Label digital image with location/image number.
- Complete all required data collection forms.

# 5.4.2 Laboratory Procedures

- Record results of dipstick urinalysis and process urine culture if dipstick positive for UTI.
- Record vaginal pH measurement.
- Examine wet mount by direct microscopy to detect *T. vaginalis*, *C. albicans* infections, and clue cells for BV.
- Conduct LCR for *N. gonorrhoeae* and *C. trachomatis* if symptomatic.
- If ulcerative lesion was observed, conduct dark field microscopy of swab and serology (RPR with confirmation by FTA-ABS or TP/HA) for *T. pallidum* and prepare and ship swabs to the HPTN Central Lab for M-PCR.
- Store unstained dried smear for Gram staining and batch analysis using the Nugent criteria for BV.

# 5.5 Day 7 Follow-up Visit for Female Participants (Target Day 7, allowable Day 5-9)

This visit is scheduled to take place on study Day 7. Every effort should be made to complete this visit on Day 7, however the visit may take place — if necessary —between Days 5 and 9. As described below, the baseline evaluations completed at the study Screening and Enrollment Visits are repeated at this visit, with the exception that colposcopy is performed only if abnormalities are observed on speculum exam. Diagnosis and follow-up of any observed abnormalities will proceed according to Appendix III.

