# 2.3 Study Design

This is an open-label Phase I study of 0.5% PRO 2000/5 Gel (P) to be conducted among 60 HIV-uninfected sexually active women from Pune, India. The male partners of these women also will be enrolled in the study. Half of the female participants will be at low risk for HIV infection; the other half will be at higher risk (see Sections 3.1.2 and 3.2.2 for definitions of low and higher risk). Both low and higher risk participants will apply 0.5% PRO 2000/5 Gel (P) twice daily for 14 consecutive days between menses, and agree to have vaginal intercourse with a single male partner, using study-provided male condoms, at least twice per week during the two weeks of product application.

After providing written informed consent, female participants will undergo eligibility screening, including medical history, pelvic exam, Pap smear (if there is no documented normal Pap in the past three months), urine pregnancy testing, HIV and STD counseling and testing, hematology and coagulation testing, and liver and renal function testing. For participants who are presumptively eligible at this visit, an Enrollment Visit will be scheduled to take place 2-7 days after the participant's next menstrual period, but within 30 days of initial screening. In addition, the participant's male sexual partner will be informed of the study and its requirements of him, asked to

provide written informed consent to take part, and be screened for eligibility. Female participants whose male partners are not willing to provide written informed consent, or are not found to be eligible, will not be eligible to take part in the study. Female participants in a previous microbicide study in Pune indicated that they would not participate without the knowledge of their male partners due to concerns over domestic violence.

At their Enrollment Visits, female participants will be provided their screening test results. Presumptively-eligible participants will undergo a pelvic exam with colposcopy, and urine pregnancy testing to confirm their eligibility. Hematology, coagulation, and liver and renal function testing will be performed, and plasma will be collected and stored for batch testing for PRO 2000/5 drug levels at the end of the study. In addition, participants will be provided with:

- Supplies of 0.5% PRO 2000/5 Gel (P), applicators, panty liners, and male condoms;

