# 5.6 Day 14 Follow-up Visit for Female Participants (Target Day 14, allowable Day 12-16)

This visit is scheduled to take place on study Day 14. Every effort should be made to complete this visit on Day 14, however the visit may take place — if necessary —between Days 12 and 16. As described below, the baseline evaluations completed at the study Screening and Enrollment Visits, including routine colposcopy, are repeated at this visit. Diagnosis and follow-up of any observed abnormalities will proceed according to Appendix III.

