#### 6.0 Adverse Event Reporting Requirements

An AE is defined as any untoward medical occurrence in a clinical research participant administered an investigational product and which does not necessarily have a causal relational with the investigational product. As such, an AE can be an unfavorable or unintended sign (including an abnormal laboratory finding, for example), symptom or disease temporally associated with the use of an investigational product, whether or not considered related to the product.

Study participants will be provided a 24-hour telephone number and instructed to contact the study clinician to report any AEs they may experience, except for life-threatening events, for which they will be instructed to seek immediate emergency care. Depending on the severity of the event, the clinician will instruct the participant to present to the study site (for more mild events) or to an emergency room (for more serious events) for immediate evaluation. Where feasible and medically appropriate, participants will be encouraged to seek medical care where the study clinician is based, and to request that the clinician be paged or otherwise contacted upon their arrival. With appropriate permission of the participant, records from all non-study medical providers related to AEs will be obtained and required data elements will be recorded on study case report forms. All participants reporting an AE will be followed clinically, until the AE resolves (returns to baseline) or stabilizes.

Study site staff will document on study case report forms all AEs reported by or observed in enrolled study participants regardless of severity and presumed relationship to study product. All AEs will be defined as described in the DAIDS HPTN SAE Reporting Manual (dated June 1, 2001). All AEs will be graded using the DAIDS Table for Grading Severity of Adverse Experiences (also referred to as the "Toxicity Table"). Both the DAIDS SAE Reporting Manual and the Toxicity Table are provided in the studyspecific procedures manual. The investigator or designee will assess the relationship of all AEs to the study product based on the DAIDS HPTN SAE Reporting Manual, the Investigator's Brochure, and his/her clinical judgment.

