#### 7.0 Statistical Considerations

#### 7.1 General Design

This is a Phase I open-label study with 14 days of twice daily application of 0.5% PRO 2000/5 Gel (P) and follow-up for each study participant. Safety will be assessed after 7 and 14 days of product use. Acceptability measures will be assessed at baseline and after 14 days of product use via standardized questionnaire; additional acceptability information will be collected through focus groups with female study participants and their male sexual partners conducted approximately 2-3 weeks after completing the product use regimen.

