#### 7.4.1 Primary Analyses

Primary data analyses will tabulate the number of primary endpoints listed in Section 7.1.1 — observed during the study. All participants who enroll in the study will be included in each tabulation. Individual participants will contribute once to the calculation of event rates. Additional safety analyses will tabulate the number and type of AEs observed overall and by severity and relationship to product. AEs that lead to discontinuation of product use and/or study participation will be tabulated separately. The temporal relationship of product application and AE onset, and the duration of symptoms, also will be evaluated. Finally, baseline and Day 14 laboratory measures will be summarized and the change in function, defined as the difference between the baseline and Day 14 measurements, will be described.

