## **Appendix VIII: Analysis Tables**

- 1. Study completion number and percentage of subjects completing the study. Day of discontinuation.
- 2. Baseline demographics descriptive summaries of demographic characteristics.
- 3. Pelvic exam at baseline descriptive summaries of pelvic exam variables at baseline.
- 4. Colposcopic exam at baseline descriptive summaries of colposcopic exam at baseline.
- 5. Laboratory measurements at baseline descriptive summaries of laboratory measurements.
- 6. Acceptability at baseline descriptive summaries of acceptability variables at baseline.
- 7. Adherence descriptive summaries of adherence.
- 8. Protocol deviations descriptive summaries of protocol deviations.
- 9. Pelvic exam at Day 2, Day 7, and Day 14 descriptive summaries of pelvic exam variables at Day 2, Day 7, and Day 14.
- 10. Change in selected pelvic exam variables from baseline to Day 2, Day 7 or Day 14 change from baseline to Day 2, Day 7, and Day 14 pelvic exam variables.
- 11. Colposcopic exam at Day 2 and Day 14 descriptive summaries of colposcopic exam at Day 2 and Day 14.
- 12. Change in selected colposcopic exam variables from baseline to Day 2 and Day 14 baseline, Day 2, and Day 14 colposcopic exam variables.
- 13. Treatment emergent adverse events number of subjects experiencing adverse events while on treatment by MeDRA SOC and preferred term. Summaries will be given by severity and by relationship to study treatment.
- 14. Change in selected AEs from baseline to Day 2, Day 7, and Day 14 number and percentage of subjects experiencing AEs at baseline and at Day 2, Day 7, and Day 14 follow-up visits.
- 15. Laboratory data at Day 14 descriptive summaries of laboratory measurements.

- 16. Change in laboratory data descriptive summaries of the change in laboratory measurements from baseline to Day 14.
- 17. Acceptability at Day 14 descriptive summaries of acceptability variables at and Day 14.
- 18. Change in acceptability variables from baseline to Day 14 baseline and Day 14 acceptability variables.
- 19. Concomitant medications descriptive summaries of concomitant medications at baseline, Day 2, Day 7, and Day 14.

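### Findings visible only by colposcopy are less likely to be detected at Day 7 than at Days 0, 2 and 14, but the by-visit AE table and the AE-onset evaluation do not allow for this

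*Protocol*

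**What the plan says.** **Examination schedule.** At enrollment, "Presumptively-eligible participants will undergo a pelvic exam with colposcopy" (Protocol 2.3). At Day 2 the instruction is "Perform pelvic examination with colposcopy (according to Appendix V) including" a list of colposcopic steps (5.4.1). At Day 14 the baseline evaluations, "including routine colposcopy, are repeated at this visit" (5.6). At Day 7 "colposcopy is performed only if abnormalities are observed on speculum exam" (5.5); Section 2.3 says the same, and Appendix I marks Day 7 colposcopy as done if indicated.

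**What counts as an AE.** Section 6.0 includes unfavorable signs and requires staff to document "all AEs reported by or observed in enrolled study participants regardless of severity". A lesion seen only under the colposcope therefore qualifies.

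**Planned analyses.**
- Appendix VIII items 9 and 10 summarize pelvic exam variables at Days 2, 7 and 14. Items 11 and 12 summarize colposcopic variables at Days 2 and 14 only.
- Item 14, on change in selected AEs, gives the "number and percentage of subjects experiencing AEs at baseline and at Day 2, Day 7, and Day 14 follow-up visits".
- Section 7.4 assigns McNemar's test to categorical changes from baseline.
- Section 7.4.1 adds: "The temporal relationship of product application and AE onset, and the duration of symptoms, also will be evaluated".
- Section 7.1 names Day 7 as a safety time point, "Safety will be assessed after 7 and 14 days of product use", without noting that the examination differs between the two days.

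**The concern.** Appendix VIII already separates the two kinds of examination in items 9 to 12. Item 14 then puts AEs from either source into one by-visit comparison that includes Day 7. Nothing in the protocol says how colposcopy-only findings are treated in that column or how their onset is dated.

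Two readings are at risk. A lower Day 7 figure could be taken as tolerance after the first days of use, when part of it reflects a less sensitive examination. A lesion that began in the first week but was first seen at Day 14 could be taken as late toxicity. The trial has a single arm, so no control group with the same schedule would reveal such a pattern as an artefact.

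**Working it through.** The protocol states no figure on this point. Its nearest figures, the probabilities of two or more events among 60 women in 7.2, reproduce from the exact binomial: 0.121, 0.808, 0.929, 0.986, 0.999 and 1.000 at true rates of 1, 5, 7, 10, 15 and 20%. No stated number is in error.

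**Inputs**
- n = 60 women (7.2).
- p = true prevalence, at a visit, of women with an exam-detectable genital finding. Assumed 10% or 20% and equal at Days 2, 7 and 14.
- c = share of those women whose findings show only under the colposcope. Not in the documents; assumed 0 to 75%.

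**Expected counts.** At Days 2 and 14: n × p. At Day 7: n × p × (1 − c). Shortfall: n × p × c.

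| p | Days 2 and 14 | Day 7, c = 0 | c = 25% | c = 50% | c = 75% |
|---|---|---|---|---|---|
| 10% | 6.0 | 6.0 | 4.5 | 3.0 | 1.5 |
| 20% | 12.0 | 12.0 | 9.0 | 6.0 | 3.0 |

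For c between 25% and 50%, the shortfall runs from 60 × 0.10 × 0.25 = 1.5 women to 60 × 0.20 × 0.50 = 6 women. It is zero at c = 0 and cannot be negative.

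**Is an observed dip certain?** Treat the Day 2 and Day 7 counts as independent binomials (a simplification, because the visits are paired). The chance that the Day 7 count is below the Day 2 count is 63% and 81% at p = 10% (c = 25% and 50%), and 73% and 92% at p = 20%. With c = 0 it is 44% and 45%. For c = 25% and 50%, the chance that Day 7 is above Day 2 is still 26% and 11% at p = 10%, and 20% and 4.5% at p = 20%. Detection is lower by design; the observed rate need not be.

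**Paired test against baseline.** A colposcopy-only finding present at baseline and persisting at Day 7 can be scored as resolved. One that is new at Day 7 can be scored as absent at both visits. Both errors push the baseline-to-Day 7 change toward improvement.

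**Onset dating.** Routine colposcopies after baseline fall on Day 2 and on Day 14 (allowable Days 12–16). The onset of a colposcopy-only lesion first seen at the last visit is known only to within 14 − 2 = 12 days (10 to 14 with the window), against a product-use period of 14 days.

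**The case against.** The strongest case against is that little of the plan is touched.

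- Item 14 covers selected AEs and does not say which. That choice may properly be left to the SAP. If only symptoms and speculum-visible signs are selected, the table has no artefact. This stands, and it makes the point conditional on what is selected.
- Duration in 7.4.1 concerns symptoms, which women enter on Daily Study Records (4.5). Those dates do not depend on colposcopy. This stands; only the onset of asymptomatic colposcopic findings is affected.
- Interim visits for genital symptoms include colposcopy (5.7), AEs are followed until they resolve or stabilize (6.0), and Appendix III re-evaluates several findings within 48 to 72 hours. A lesion found at Day 2 does not simply disappear from the record. This largely stands, although several of those re-evaluations are specified as speculum exams, which may not show whether a colposcopy-only finding persists. The main gap is asymptomatic lesions arising after Day 2.
- The primary endpoints are macroscopic damage and laboratory toxicity (7.1.1), and each woman counts once (7.4.1). This stands.

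A reader might go further and infer that Day 7 rates must dip, or that AE counts would appear to double from Day 7 to Day 14. The documents do not support that. True rates may change with exposure, and Day 7 to Day 14 is not a planned contrast. Nor can the 16% abrasion figure in 1.2.2 serve as a per-visit prevalence: it is the share of women over a whole study of 2% and 4% gel, where half of the epithelial disruption findings had another possible explanation. In the earlier placebo-controlled trials described there, none of the three cervical abrasions was in the 0.5% group (24 women), though those women were abstinent and dosed once daily.

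**Conclusion.** The point holds in a limited form. For any exam-detected genital AE included in item 14 or in the onset evaluation, detection at Day 7 is lower than or equal to that at baseline, Day 2 and Day 14 by design. Lesions visible only by colposcope that arise after Day 2 may be dated to Day 14 or, if healed by then, never counted. Items 11 and 12 show that the plan recognizes the difference; item 14 and 7.4.1 do not carry it through.

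The direction is certain and the size is not. The 1.5 to 6 of 60 women is an illustration resting on assumed prevalence, an assumed colposcopy-only share and equal true prevalence across visits; zero remains possible. Symptom-reported AEs, speculum-visible signs and symptom duration are not affected, and the primary tabulation largely is not. This is a cheap improvement to secondary safety summaries and does not threaten the main safety result.

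**What to change.** 1. On the case report form, record for each genital finding whether it was seen by naked eye or speculum, or only by colposcope. Appendix V already puts the naked-eye look before magnification.
2. In item 14 and the 7.4.1 onset evaluation, limit comparisons involving Day 7 to symptoms and naked-eye findings.
3. Show colposcopy-only findings for baseline, Day 2 and Day 14 only, as items 11 and 12 do.
4. Report the onset of a colposcopy-only finding as the interval from the last colposcopy without it to the first with it.

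The cost is one extra form item, a few lines in 7.4.1 and Appendix VIII, and a by-visit AE table split in two. No examination is added and clinical management is unchanged.
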